## 1. OBJECTIVES

### 1.1 Primary Objectives

- 1.1.1 To assess the retention rate of patients at 10 weeks of Ramipril treatment (6 weeks during RT and 4 weeks post RT) to determine whether or not we should proceed to a subsequent randomized study. Retention is defined by (1) compliance with drug therapy for at least 75% of doses during the 10 week period and (2) completion of the composite neurocognitive battery.
- 1.1.2 To estimate the effect of 10 weeks of Ramipril on neurocognitive function in patients with GBM receiving chemoradiotherapy. Neurocognitive function is measured by the Clinical Trial Battery Composite (CTB COMP) score.

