Optune® with adjuvant temozolomide in patients with newly diagnosed supratentorial glioblastoma is listed as a level 1 recommendation by the NCCN guidelines and has been adopted by many, but not nearly all, medical practitioners who treat these patients. Currently, a minority of newly diagnosed glioblastoma patients are either offered or choose to accept this treatment modality due to patient or provider preferences, or established contraindications to use which include the presence of implantable electronic devices, allergy to the array’s conductive hydrogel adhesive or the presence of cranial defects. Optune® may only be prescribed by qualified physicians who have completed a training course given by Novocure (the device manufacturer). Of note, as prescribed in the pivotal clinical trial referenced above, standard practice is to apply the Optune® device no sooner than 4 weeks after the completion of concurrent radiation and temozolomide chemotherapy.

For patients enrolled on this trial, Optune® may be used at the discretion of the treating physicians as per standard of care guidelines, timing and training. Use will be captured and an exploratory analysis of primary and secondary objectives based on the subgroups using and not using the device will be performed.

**Drug:** Ramipril (e.g. Altace® or Tritace®) is an ACE-I. It is currently FDA approved for use in the treatment of hypertension and for reducing the risk of myocardial infarction, stroke and death from cardiovascular causes. The drug will be obtained, packaged, and distributed by McKesson Corporation (Winston-Salem, NC). McKesson Corp. will also provide storage and inventory for the study drug. Ramipril will be provided to study participants at no cost.

**Assessment plan:** Participants will complete the entire battery of neurocognitive tests and questionnaires measuring cognitive symptoms, mood, fatigue, sleep disturbance and quality of life at baseline, at the completion of RT, 1 month post-RT, and q3 monthly thereafter up to 4 months post-RT or until time of

tumor progression. At the end of radiation and at the one and four-month post-RT follow-up visit, patients' tolerance of medication and compliance will be assessed by a research team member at an in-person visit coordinated with clinical follow-up. Patients are encouraged to call at any time for questions regarding study drug and will fill out a diary to document study drug compliance.

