## **4. PARTICIPANT SELECTION**

### **4.1 Inclusion Criteria**

- 4.1.1** Histologically proven diagnosis of glioblastoma or gliosarcoma (WHO grade IV) obtained at the time of a partial or gross total resection of the tumor. Patients who undergo a stereotactic needle biopsy alone are not eligible.
- 4.1.2** The tumor must have a supratentorial component.
- 4.1.3** History/physical examination within 14 days prior to enrollment
- 4.1.4** The patient must have recovered from the effects of surgery, postoperative infection, and other complications before enrollment.
- 4.1.5** Patient planning to receive brain RT, and concurrent and adjuvant temozolomide chemotherapy for 6 weeks as per standard of care therapy. Use of the Optune® (also known as Tumor Treating Fields or TTFields) device is allowed at provider discretion, but must begin after the Month 1 Post RT (10 wk) Neurocognitive-PRO assessment.
- 4.1.6** Study drug (Ramipril) must be given  $\geq 21$  days and  $\leq 42$  days after surgery.
- 4.1.7** All available brain MRI or CT imaging reports from surgery to study completion must be submitted. This includes any post-operative or pre-radiation scan reports.
- 4.1.8** ECOG 0, 1 or 2;
- 4.1.9** Age  $\geq 18$ ;
- 4.1.10** CBC/differential obtained within 14 days prior to enrollment, with adequate bone marrow function defined as follows:
  - Absolute neutrophil count (ANC)  $\geq 1,500$  cells/mm^3;
  - Platelets  $\geq 100,000$  cells/mm^3;
  - Hemoglobin  $\geq 10.0$  g/dl (Note: The use of transfusion or other intervention to achieve Hgb  $\geq 10.0$  g/dl is acceptable.)
- 4.1.11** Adequate renal function, as defined below:
  - BUN  $\leq 30$  mg/dl within 14 days prior to enrollment.
  - Creatinine  $\leq 1.7$  mg/dl within 14 days prior to enrollment.
- 4.1.12** Adequate hepatic function, as defined below:
  - Total Bilirubin  $\leq 2.0$  mg/dl within 14 days prior to enrollment.
  - ALT/AST  $\leq 3$  x normal range within 14 days prior to enrollment.

- 4.1.13** Patient must provide study specific informed consent prior to study entry.

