## **12.2 Accrual and Feasibility**

### **Sample Size**

We will assess the dropout rate to inform us regarding the design of a subsequent randomized study. We will test the null hypothesis that retention  $< 65\%$  versus the alternative hypothesis that retention  $\geq 65\%$ , with 90% power for detecting an alternative retention of 80%. The 65% threshold is related to retention rate, and is different from the 75% of doses required for compliance (Section 12.1). Assuming a 1-sided test at the 0.05 significance level, we obtain a sample size of 75 participants. The sample size calculation was conducted using NQuery Advisor v7.0. Based on this calculation, we will plan for a sample size of 75, which will allow us to determine with a high level confidence whether or not the retention rate is sufficient to justify a subsequent study to this pilot.

We will also estimate the effect size in terms of reduction in neurocognitive decline in the intervention group as compared to historical controls. No formal statistical hypothesis will be tested for the purpose of declaring efficacy. The effect size, along with the estimate of the dropout rate, will be used to power and assess the feasibility of a planned subsequent randomized study. We expect an accrual rate of approximately 4 per month based on prior NCORP studies in similar brain tumor populations.

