Treating physician response rate will be summarized at each timepoint with corresponding 95% confidence intervals. Time to neurocognitive failure will largely follow the method reported in Gilbert *et al.* for evaluating if there is meaningful difference in the risk of cognitive progression. Neurocognitive failure will be defined as the first decline on reliable change index on any of the individual cognitive tests. In the presence of competing risks for neurocognitive failure, including GBM-related mortality risk, we plan to explore the use of competing risks methods for both descriptive statistics (e.g. the Kaplan-Meier curves) and competing risk regression analysis. Competing risk methods are needed because time to neurocognitive failure is not independent of mortality and ignoring events from competing risk will lead to biased results. The competing risk analysis will be based on the method proposed in Gray and Fine and Gray using SAS macro %CIF and PROC PHREG. Patient reported outcomes will be assessed as described above for the CTB COMP.

Exploratory subgroup analyses will be conducted for all 4 month post RT outcomes by whether the patient received Optune® (also known as Tumor-Treating Fields or TTFIELDS) as part of their standard treatment following RT. Differences by Optune® for continuous outcomes will be assessed by two-sample t-tests where parametric assumptions hold; otherwise Mann-Whitney U tests will be applied. For categorical outcomes, Fisher's exact or Chi-square tests will be implemented. Corresponding 95% confidence intervals will also be presented for outcomes within each subgroup.

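### Optune subgroups: two sections extend the comparison to primary endpoints that precede device use, and the 4-month comparison is unadjusted for who receives the device

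*Combined protocol and SAP*

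**What the plan says.** **Scope.** Section 3 (Optune paragraph) and Section 5.1.1.3 carry the same sentence, promising an "exploratory analysis of primary and secondary objectives based on the subgroups using and not using the device". Objective 1.3.1 is narrower: secondary objectives at the 4-month post-RT visit. Sections 12.1 and 12.4 likewise speak only of 4-month outcomes.

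**Timing.** The first primary objective is "To assess the retention rate of patients at 10 weeks of Ramipril treatment" and the second is "To estimate the effect of 10 weeks of Ramipril on neurocognitive function in patients with GBM receiving chemoradiotherapy". Section 8.1 places both at Week 10. Criterion 4.1.5 says device use "must begin after the Month 1 Post RT (10 wk) Neurocognitive-PRO assessment"; exclusion 4.2.15 and Section 5.1.1.3 are consistent with this.

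**Denominator.** Under Section 12.3, every patient who takes at least one dose of ramipril is evaluable for retention, so early dropouts count.

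**Allocation.** Section 3 leaves the device to the treating physician. It says that only a minority of patients are offered or accept it, because of preferences or contraindications. It gives no percentage.

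**Method.** In Section 12.4, Optune differences in "continuous outcomes will be assessed by two-sample t-tests where parametric assumptions hold", with Mann-Whitney otherwise, and Fisher or chi-square for categorical outcomes. No covariate, Week 10 score or landmark is named. The covariates in the same section (MGMT methylation, KPS, extent of resection) are there for differences from the RTOG 0825 cohort.

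**The concern.** There are two separate problems.

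First, a statistician cannot follow both statements of scope, and the wider one cannot be interpreted. Anyone who dies, withdraws or misses the battery before the Week 10 assessment fails retention and, if the rules are followed, cannot become a user within the study. Subgroup membership is then partly decided by the outcome being compared.

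Second, the 4-month comparison is between patients who were offered and accepted a device and patients who were not. Fitness, staying progression-free until the device can start, and preference all plausibly relate to cognition at 4 months. An unadjusted test reports their combined effect under the device's name. At stake is a misleading exploratory result in a pilot meant to inform the design of a randomised trial.

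**Working it through.** **1. The plan's own figure.** The inputs are in Section 12.2: null retention 65%, alternative 80%, power 90%. The plan states: "Assuming a 1-sided test at the 0.05 significance level, we obtain a sample size of 75 participants". With null and alternative variances, n = [(1.645 x sqrt(0.65 x 0.35) + 1.282 x sqrt(0.80 x 0.20)) / 0.15]^2 = 74.8, rounded up to 75. An exact binomial test rejecting at 56 or more of 75 has alpha 0.0485 and power 0.900. The figure reproduces. It is for retention in the whole sample; no size or power is given for Optune subgroups.

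**2. Retention by device, limiting case.** Let R be overall retention and f the share of retained patients who go on to Optune. Assume that nobody else uses it. Users are then 100% retained and non-users (R - Rf)/(1 - Rf), so the gap is (1 - R)/(1 - Rf).

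- R = 0.75, f = 0.30: 0.525/0.775 = 67.7% in non-users, a gap of 32.3 points.
- R = 0.80, f = 0.20: 0.20/0.84 = 23.8 points (smallest on the grid R = 65-80%, f = 20-40%).
- R = 0.65, f = 0.40: 0.35/0.74 = 47.3 points (largest).

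**3. Retention by device, softer case.** A patient who took under 75% of doses can still complete the Week 10 battery and then start the device. With 60 of 75 retained (80%), and users now counted as a share of all 75:

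| Users | All users retained | About 10% of users miss the dose criterion |
|---|---|---|
| 15 (20%) | 100% vs 45/60 = 75.0%; p = 0.03 | 14/15 = 93.3% vs 46/60 = 76.7%; gap 16.7; p = 0.28 |
| 22 (29%) | 100% vs 38/53 = 71.7%; p = 0.004 | 20/22 = 90.9% vs 40/53 = 75.5%; gap 15.4; p = 0.21 |
| 30 (40%) | 100% vs 30/45 = 66.7%; p = 0.0002 | 27/30 = 90.0% vs 33/45 = 73.3%; gap 16.7; p = 0.14 |

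The p-values are Fisher exact. At lower overall retention the softer gap grows: 23-26 points with 56 of 75 retained and 35-41 points with 49 of 75. The device has no effect in any of these cases.

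**4. Four-month scores.** A simulation set the true device effect to zero, with N = 75, 30% base uptake and a two-sample t-test. All selection strengths are assumptions.

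| Assumed selection | Spurious difference | False-positive rate |
|---|---|---|
| Uptake unrelated to fitness, with or without 20-35% fitness-related attrition | about 0 SD | about 5% |
| Uptake rises with fitness, log-odds 0.5 to 1.0 per SD | 0.34-0.64 SD | 21-76% |
| 10-30% progress before they can start and score 0.8 SD lower | 0.07-0.22 SD | 6-10% |

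The first row shows that attrition shared by both groups creates no false effect. The other rows show that selection into device use does. In the second scenario, the Week 10 scores already differ by 0.37-0.65 SD, before any device use.

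**5. Precision.** The 95% half-width is 1.96 x sqrt(1/n_user + 1/n_non-user). With 75 scored and 30 users it is 0.46 SD; with 50 scored and 10 users, 0.69 SD.

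**The case against.** The strongest reply is that the analysis is exploratory, that Section 12.2 tests no efficacy hypothesis, and that the stated objective and the only section with Optune methods already limit it to 4-month outcomes. That stands. A reader might infer that the sponsor has settled on testing primary endpoints by device; the documents support only an internal conflict, two narrative sections against 1.3.1, 12.1 and 12.4. It still needs resolving, because the wider wording appears twice.

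A reader might also call the 4-month problem survivor selection. It is not. Objective 1.2.4 concerns surviving patients, and everyone with a 4-month score, user or not, lived past Week 10. Section 3 also schedules testing only until progression, which may already limit scores from progressors. What remains is confounding by who gets the device. It could bias the result; the documents do not show that it will. The Mann-Whitney alternative changes the distributional assumption and leaves the confounding in place.

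The 24-47 point range should not be read as the expected gap, since it needs every user to be retained. The gap narrows as more non-retained patients stay on study and use the device, and the documents give no split of reasons for non-retention.

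Nor does any section tie the Optune result to device policy in the next trial. Section 12.2 rests that trial on the effect size against historical controls and the dropout rate.

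Finally, with intervals this wide, purely descriptive reporting would also be defensible. Adjustment is preferable because the pre-device score is already collected.

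**Conclusion.** The point holds in a limited form. The scope conflict is a matter of text and needs no assumption. That the device cannot affect either primary endpoint follows from the protocol's own timing rule. The direction of the retention artefact follows too, provided that some non-retained patients are lost before the Week 10 assessment. Its size is assumption-dependent: 24-47 points in the limiting case, and about 15-17 points at 80% retention with roughly 10% of users missing the dose criterion. Uptake of 20-40% is assumed throughout.

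For 4-month scores, the unadjusted comparison could show selection into device use as a device effect. The simulated 0.34-0.64 SD illustrates what moderate to strong selection would do; it does not estimate what will occur. The sample size of 75 and the primary retention analysis are unaffected. The change is worth making because it is cheap, but no efficacy decision depends on it.

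**What to change.** 1. In Sections 3 and 5.1.1.3, delete the words *primary and*, so that they agree with 1.3.1, 12.1 and 12.4, and refer to 4-month outcomes.
2. In Section 12.4, for continuous 4-month outcomes, replace the unadjusted test with ANCOVA of the 4-month score on device use. Restrict it to patients tested and progression-free at Week 10, and adjust for the Week 10 (pre-device) score and baseline performance status. Report the estimate with a 95% interval.
3. Describe the result as exploratory, non-randomised and subject to residual confounding, including from events between Week 10 and device start. Give the categorical comparisons the same caveat. Adjustment reduces the bias but cannot remove it.

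Section 7.1 already schedules what is needed: cognitive and quality-of-life scores at Week 10, ECOG at baseline, device use from Week 10, and physician-assessed response for each scan. The cost is protocol and analysis-plan wording, plus a slightly smaller analysed number because of the landmark.

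A sensitivity analysis of the RTOG 0825 comparison without Optune users is not recommended. It would condition on a post-baseline choice in one cohort only and could remove the fitter ramipril patients.

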## **4. PARTICIPANT SELECTION**

### **4.1 Inclusion Criteria**

- 4.1.1** Histologically proven diagnosis of glioblastoma or gliosarcoma (WHO grade IV) obtained at the time of a partial or gross total resection of the tumor. Patients who undergo a stereotactic needle biopsy alone are not eligible.
- 4.1.2** The tumor must have a supratentorial component.
- 4.1.3** History/physical examination within 14 days prior to enrollment
- 4.1.4** The patient must have recovered from the effects of surgery, postoperative infection, and other complications before enrollment.
- 4.1.5** Patient planning to receive brain RT, and concurrent and adjuvant temozolomide chemotherapy for 6 weeks as per standard of care therapy. Use of the Optune® (also known as Tumor Treating Fields or TTFields) device is allowed at provider discretion, but must begin after the Month 1 Post RT (10 wk) Neurocognitive-PRO assessment.
- 4.1.6** Study drug (Ramipril) must be given  $\geq 21$  days and  $\leq 42$  days after surgery.
- 4.1.7** All available brain MRI or CT imaging reports from surgery to study completion must be submitted. This includes any post-operative or pre-radiation scan reports.
- 4.1.8** ECOG 0, 1 or 2;
- 4.1.9** Age  $\geq 18$ ;
- 4.1.10** CBC/differential obtained within 14 days prior to enrollment, with adequate bone marrow function defined as follows:
  - Absolute neutrophil count (ANC)  $\geq 1,500$  cells/mm^3;
  - Platelets  $\geq 100,000$  cells/mm^3;
  - Hemoglobin  $\geq 10.0$  g/dl (Note: The use of transfusion or other intervention to achieve Hgb  $\geq 10.0$  g/dl is acceptable.)
- 4.1.11** Adequate renal function, as defined below:
  - BUN  $\leq 30$  mg/dl within 14 days prior to enrollment.
  - Creatinine  $\leq 1.7$  mg/dl within 14 days prior to enrollment.
- 4.1.12** Adequate hepatic function, as defined below:
  - Total Bilirubin  $\leq 2.0$  mg/dl within 14 days prior to enrollment.
  - ALT/AST  $\leq 3$  x normal range within 14 days prior to enrollment.

- 4.1.13** Patient must provide study specific informed consent prior to study entry.
- 4.1.14** Baseline potassium level < 5.0 mEq/L. High potassium values that are thought to be a result of sample hemolysis may be repeated to determine an accurate potassium level and to determine potential study eligibility. Likewise high potassium values thought to be a result of potassium supplementation may be repeated at an appropriate time (5 half-lives after supplement discontinuation) to determine potential study eligibility.
- 4.1.15** Patient must be able to complete neurocognitive tests in the English language as they are not validated in other languages at this time.
- 4.1.16** Women of childbearing potential and male participants must practice adequate contraception.
- 4.1.17** For females of child-bearing potential, negative serum or urine pregnancy test within 14 days of enrollment
- 4.1.18** Local site must be able to follow the standard GBM radiation treatment dosimetry plan as detailed in Section 5.1.1.2
- 4.1.19** For patients who will be treated with the Optune® device in addition to standard of care radiation plus concurrent and adjuvant temozolomide, the following inclusion criteria also apply:
- Patients must have only a supratentorial glioblastoma
  - The treating physician must be a qualified provider having successfully completed the training course provided by Novocure, the device manufacturer
- 4.1.20** Patients with prior malignancies if all treatment for that malignancy was completed at least 2 years before registration and the patient has no evidence of disease.

## **4.2 Exclusion Criteria**

- 4.2.1** Prior allergic reaction or intolerance to ACE inhibitor
- 4.2.2** Hypotension (<110 mg Hg systolic) at the time of enrollment
- 4.2.3** Renal insufficiency with creatinine clearance of <40 ml/min (at time of enrollment)
- 4.2.4** Solitary kidney or known renal artery stenosis
- 4.2.5** Current ACE inhibitor or angiotensin receptor blocker use. Patients can come off ACE inhibitors or angiotensin receptor blockers for 1 week to be eligible for this study.
- 4.2.6** Prior invasive malignancy (except for non-melanomatous skin cancer) unless disease free for ≥ 2 years. (For example, carcinoma in situ of the breast, oral cavity, and cervix are all permissible).
- 4.2.7** Recurrent or multifocal malignant gliomas

- 4.2.8** Metastases detected below the tentorium or beyond the cranial vault.
- 4.2.9** Prior chemotherapy or radiosensitizers for cancers of the head and neck region; note that prior chemotherapy for a different cancer is allowable, except prior temozolomide. Prior use of Gliadel wafers or any other intratumoral or intracavitary treatment are not permitted.
- 4.2.10** Prior radiotherapy to the head or neck (except for T1 glottic cancer), resulting in overlap of radiation fields.
- 4.2.11** Severe, active co-morbidity, defined as follows:
- Acute bacterial or fungal infection requiring intravenous antibiotics at the time of enrollment
  - Chronic obstructive pulmonary disease exacerbation or other respiratory illness requiring hospitalization or precluding study therapy at the time of enrollment.
  - Known HIV positivity or acquired immune deficiency syndrome (AIDS) based upon current CDC definition; note, however, that HIV testing is not required for entry into this protocol. The need to exclude patients with AIDS from this protocol is necessary because the treatments involved in this protocol may be significantly immunosuppressive.
  - Active connective tissue disorders, such as lupus or scleroderma, that in the opinion of the treating physician may put the patient at high risk for radiation toxicity.
  - Any other major medical illnesses or psychiatric impairments that in the investigator's opinion will prevent administration or completion of protocol therapy.
- 4.2.12** Pregnancy or women of childbearing potential and men who are sexually active and not willing/able to use medically acceptable forms of contraception; this exclusion is necessary because the treatment involved in this study may be significantly teratogenic.
- 4.2.13** Pregnant or lactating women, due to possible adverse effects on the developing fetus or infant due to study drug.
- 4.2.14** Patients treated on any other therapeutic clinical protocols within 30 days prior to study entry or during participation in the study unless they involve standard of care or over the counter therapies or do not involve a drug therapy. Questions regarding eligibility for patients enrolled on other therapeutic clinical trials should be forwarded to the Wake Forest NCORP Research Base email ([[contact]](mailto:[contact])) for review.
- 4.2.15** Patients planning to receive therapeutic antitumor agents (excluding use of the Tumor Treating Fields (TTFields or Optune®) device after the Month 1 Post RT (10 wk) Neurocognitive-PRO assessment) in addition to standard radiation and concurrent and adjuvant temozolomide are not eligible to participate in this study.
- 4.2.16** Patients with impaired decision-making capacity; this exclusion is necessary because such patients may not be able to adequately give informed consent.

**4.2.17** For patients who will be treated with the Optune® device in addition to standard of care radiation plus concurrent and adjuvant temozolomide, the following exclusion criteria also apply:

- Optune® is not permitted in patients who have an active implanted medical device, skull defect (such as, missing bone with no replacement) or bullet fragments. Examples of active electronic devices include deep brain stimulators, spinal cord stimulators, vagus nerve stimulators, pacemakers, defibrillators, and programmatic shunts.
- Optune® is not permitted in patients who are known to be sensitive to conductive hydrogels. Examples of conductive hydrogels are gels used on electrocardiogram (ECG) stickers or transcutaneous electrical nerve stimulation (TENS) electrodes.

**4.2.18** Patients being treated with Memantine, Donepezil, and/or other medications prescribed to enhance cognition.

